## **STUDY DESIGN AND METHODS**

Prospective, randomized, placebo-controlled, cross-over study

Inclusion Criteria:

1. Men and women 35 – 70 years of age
2. Overweight or obese subjects with BMI ranging from 25 - 37 kg/m^2.
3. Subjects will have pre-diabetes defined as fasting glucose  $\geq 100$  mg/dL or a 2-hour glucose value  $\geq 140$  mg/dl during an oral glucose tolerance test (OGTT)

OR

Mild diabetes defined as patients with a Hba1c  $\leq 7\%$  on no medications (diet-controlled) or on a stable dose of metformin and no other hypoglycemic agents for  $\geq 3$  months before study entry.

4. Willing and able to comply with study requirements.

Exclusion Criteria:

1. Pregnancy and lactation
2. Change in dose of metformin or use of hypoglycemic agents other than metformin for treatment of diabetes within 3 months of study entry. Diagnosis of diabetes will be based on the 2011 American Diabetes Association guidelines: Hba1c  $\geq 6.5\%$ , fasting plasma glucose  $\geq 126$  mg/dl, 2-hour glucose  $\geq 200$  mg/dl during an OGTT, or a random blood glucose  $\geq 200$  mg/dl along with classic symptoms of hyperglycemia (34)
3. Uncontrolled hypertension (blood pressure  $\geq 180/110$  mmHg)
4. Current unstable medical conditions including clinically significant impaired cardiac function (Stage III and IV Cardiac failure), cardiac ischemia, severe respiratory insufficiency requiring oxygen therapy as assessed on history and/or physical exam
5. Liver function tests (ALT, AST) more than 3-times the upper normal limit
6. Severe renal impairment (creatinine clearance  $< 30$  ml/min)
7. Evidence of human immunodeficiency virus (HIV) based on history and physical examination and/or known positive HIV antibodies
8. Evidence of hepatitis C based on history and physical examination and/or known positive hepatitis C (HCV) antibody
9. History of hemorrhagic disorders or on anticoagulants
10. History of endometrial cancer, endometrial hyperplasia, unexplained vaginal bleeding, or endometrial thickness greater than 6 mm
11. Change in dose of lipid-lowering medications (including HMG Co-A inhibitors, fibrates, niacin, ezetemibe, and over-the-counter fish oil supplements) within one month of study entry and during the study period
12. Current administration of medications known to be strong CYP3A4 inhibitors including ketoconazole, itraconazole, and erythromycin
13. Use of herbal supplements or grapefruit juice within 14 days of study drug initiation
14. Use of medications or dietary supplements that inhibit or induce CYP3A4 activity within 14 days of study drug initiation
15. Use of oral, injectable, or inhaled glucocorticoids or megestrol in the past six months
16. Use of estrogen-containing hormone therapy
17. Potential pseudocushing's states: depression or intake of  $> 2$  alcoholic drinks a day for women and  $> 3$  alcoholic drinks per day for men. Subjects will be screened for depression

using the well-validated physician health questionnaire-9 (PHQ-9) with a score cut-off of  $\geq 10$  for moderate depression (35).

18. Subjects who are actively dieting or are in a weight loss program
19. Midnight salivary cortisol  $> 100$  ng/dl on two separate occasions
20. Untreated thyroid dysfunction (TSH and Free T4 not within normal range). If abnormal on screening labs, they will be repeated to confirm that not due to lab error or non-thyroidal illness.
21. Moderate to severe anemia (hemoglobin  $< 10$  g/dl)
22. Blood donation of more than 500 ml within one month prior to study enrollment
23. Subjects with a prolonged QTc interval on electrocardiogram
24. Unable to give informed consent

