## **Study protocol**

### *Screening*

[figure not shown]
Subjects will undergo evaluation at the Clinical Center for eligibility. This will include measurement of height, weight, waist circumference, blood pressure, and a detailed history and physical examination. Subjects will be screened for depression using the PHQ-9 questionnaire. If a subject is found to have severe depression or suicidal ideation, they will be seen by a psychiatrist at NIH on an emergent basis and further management will be guided by their recommendations. An electrocardiogram will be obtained to identify any subjects with QTc interval prolongation. Screening laboratory tests will include a serum pregnancy test for females, fasting plasma glucose, HgbA1c, OGTT (2 hour, after 75 g dextrose), comprehensive metabolic panel, CBC with differential, coagulation profile, midnight salivary cortisol, TSH, Free T4, FSH and LH levels. HIV 1&2 antibody and hepatitis C antibody levels will also be checked if on history taking the subject is found to have risk factors for HIV or Hepatitis C. A transvaginal ultrasound will be obtained to evaluate endometrial thickness in postmenopausal women (defined as amenorrhea for  $\geq 12$  months and an FSH level in the postmenopausal range) as well as those in the perimenopausal phase (amenorrhea for  $\geq 6$  months and FSH level in the postmenopausal range). An MRI Pelvis will be performed only if the transvaginal ultrasound is unable to provide an accurate measurement of the endometrial stripe. Subjects in whom a definite assessment of endometrial thickness cannot be obtained with either ultrasound or MRI (as may be the case in patients with multiple fibroids) will be followed closely for any signs of abnormal vaginal bleeding and will undergo a repeat transvaginal ultrasound upon completion of the study.

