## STUDY ANALYSIS

The study will be analyzed in collaboration with [name], Ph.D. (Biostatistics and Clinical Epidemiology Service, Clinical Center). Subjects will be randomized in blocks of 6 into the two treatment arms. Means and standard deviations will be used to describe continuous data. Proportions and frequencies will be used to describe categorical data. All continuous data will be examined for normality and homogeneity of variances, and will be either transformed as appropriate or assessed using non-parametric tests. The change in continuous variables (including triglyceride, HDL, LDL and total cholesterol levels, insulin sensitivity index, pre- and post-prandial glucose values, whole body cortisol production rates, blood pressure, weight, and waist circumference) before and after study intervention will be analyzed using paired t-tests or Wilcoxon signed-rank test. Correlation of continuous data (e.g., regenerated cortisol and insulin sensitivity and triglyceride levels, and mifepristone level and insulin sensitivity and triglyceride response) will be carried out by Pearson's correlation coefficient or Spearman's rho, as appropriate. Between and within treatment comparisons will be done using Mixed Models for a crossover design that will also consider sequence effect, if any. Difference in the proportion of subjects who meet criteria for metabolic syndrome, or other categorical data, before and after study intervention will be analyzed using McNemar's test. Two-sided p-values will be used for all analysis and the level of statistical significance will be set a priori at 0.05. The stepdown Bonferroni correction will be used to adjust for multiple comparisons. All statistical analysis will be performed using SAS v. 9.2 (SAS Institute, Cary, NC).

Human data on the effect of mifepristone on insulin sensitivity index are lacking. This will therefore be a pilot study of 17 subjects. Data from this study will then be used to design a long-term study looking at the effect of mifepristone on glucose intolerance, lipids, weight and blood pressure. With an estimated loss-to-follow-up rate of 15%, we would need to recruit a total of 25 patients. Thus, we plan to screen approximately 80 patients to account for the high ineligibility rate and patient drop-outs prior to study initiation.

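### Does Inclusion 3 let in subjects with HbA1c above 7% because its pre-diabetes branch has no upper glucose limit?

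*Combined protocol and SAP*

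**What the plan says.** All of this is in the combined protocol and SAP.

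- **Inclusion 3, first branch** (STUDY DESIGN AND METHODS): "Subjects will have pre-diabetes defined as fasting glucose" of 100 mg/dL or more, or a 2-hour OGTT value of 140 mg/dL or more. Both are lower bounds. The branch sets no HbA1c or medication condition.
- **Inclusion 3, second branch**, joined by OR: "Mild diabetes defined as patients with a Hba1c" of 7% or less, "on no medications (diet-controlled) or on a stable dose of metformin and no other hypoglycemic agents for" at least three months. This is an upper bound only.
- **Exclusion 2** removes subjects for "Change in dose of metformin or use of hypoglycemic agents other than metformin for treatment of diabetes within 3 months of study entry". It then adds: "Diagnosis of diabetes will be based on the 2011 American Diabetes Association guidelines", giving HbA1c of 6.5% or more, fasting glucose of 126 mg/dL or more, 2-hour glucose of 200 mg/dL or more, or a random value of 200 mg/dL or more with classic symptoms. These figures define the diagnosis; they do not exclude anyone.
- **Screening** measures fasting glucose, HbA1c and the 2-hour OGTT in every candidate and adds no cut-off.
- **STUDY ANALYSIS** describes a pilot of 17 subjects (the Precis says 15), analysed by paired tests and crossover mixed models, and states: "Data from this study will then be used to design a long-term study".

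**The concern.** The two branches are alternatives, so failing the 7% limit has no consequence for anyone who meets the first branch, and almost every subject with HbA1c above 7% will meet it. Followed to the letter, the limit acts only on people whose fasting and 2-hour glucose are both normal, who are hardly the people it was written for.

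At stake would be a population wider than the authors seem to have meant, and screening decisions that could turn on whether the screener follows the label or the numbers. Because the pilot feeds the design of a longer study, the glycaemic range it represents ought to be clear.

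**Working it through.** The plan has no figure to reproduce here; the question is one of logic. Alpha, power and sample size do not enter.

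**Rules**, for subjects on no drug or stable metformin (others fall to Exclusion 2):

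- A (first branch): fasting ≥100 or 2-hour ≥140 mg/dL.
- B (second branch): HbA1c ≤7%.
- D (laboratory thresholds in Exclusion 2): HbA1c ≥6.5%, fasting ≥126 or 2-hour ≥200 mg/dL.
- *Literal reading*: admit if A or B.
- *Reading by the labels*: if D, require B; if not D, require A.
- *First branch limited only*: if D, require B; if not D, admit if A or B.

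**Single case.** Fasting 180 mg/dL, HbA1c 9%, no drug. A holds (180 ≥ 100), B fails (9 > 7), D holds (180 ≥ 126 and 9 ≥ 6.5). Literal: admitted through A. By the labels: has diabetes, must meet B, refused.

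**Nine classes** (admitted = yes), each cell giving literal / labels / first branch limited only:

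| Glucose | HbA1c <6.5% | 6.5–7.0% | >7% |
|---|---|---|---|
| Normal | yes / no / yes | yes / yes / yes | no / no / no |
| 100–125 or 140–199 | yes / yes / yes | yes / yes / yes | yes / no / no |
| ≥126 or ≥200 | yes / yes / yes | yes / yes / yes | yes / no / no |

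Totals admitted: literal 8 of 9, labels 5 of 9, first branch limited only 6 of 9. The literal text and the labels part in three classes: two with HbA1c above 7%, and one with normal glucose and HbA1c below 6.5%. That last class enters through B, which sets no lower bound. The labels column assumes no prior diagnosis; someone with known diabetes well controlled on diet or metformin could properly enter by the second branch.

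**Check on a finer grid.** Take seven assumed fasting values (90 to 150 mg/dL), seven assumed 2-hour values (120 to 250 mg/dL), the two grid HbA1c values above 7% (7.1 and 8.0) and two permitted medication states: 7 × 7 × 2 × 2 = 196 profiles. The literal rule refuses only those with fasting below 100 (two values) and 2-hour below 140 (two values): 2 × 2 × 2 × 2 = 16. It admits 196 − 16 = 180; sorting by the labels admits 0.

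These counts describe the logic of the wording. They are not frequencies, and the documents give no distribution of screened subjects from which to derive any.

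**Does it reach the result?** Every subject receives both treatments, so glycaemic status at entry is common to both sides of the comparison and cannot be confounded with treatment. A wider range might change the spread of the insulin sensitivity response, but the documents give no variance from which to say by how much. One such subject would be 1/17 = 5.9% of the pilot (1/15 = 6.7% on the Precis figure). The primary hypothesis concerns glucose abnormalities in overweight and obese people, which such a subject has. The range actually enrolled can be tabulated from the screening results whatever the criterion says.

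**The case for a change.** The best case for a change is that the criterion defines its category by numbers, so a careful screener is entitled to apply the numbers. The competing reading borrows its thresholds from an exclusion about medication that does not refer back to Inclusion 3. An eligibility rule should not depend on that inference, the repair is one clause, and it needs no new test.

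The description of the text stands: nothing elsewhere in the document closes the gap. The practical weight does not. The criterion names pre-diabetes and mild diabetes as separate categories, and the definition of diabetes sits in the same list. A screener holding an HbA1c of 9% would have to call that subject pre-diabetic to admit him or her. The front-page listing says the project is neither off-site nor multi-institutional, which limits the scope for divergent decisions without removing it.

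The claim that the subject contradicts a study-wide limit goes too far, because the 7% figure belongs to the mild-diabetes branch alone. Subjects with diabetes are meant to be eligible; only those above 7% are in doubt. Nor would limiting the first branch make the enrolled population match the one described: on the same literal reading it still admits the class with normal glucose and normal HbA1c, which fits the Precis description of abnormal glucose tolerance less well than the subjects it removes.

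**Conclusion.** The wording is loose in both branches of Inclusion 3, and read literally it admits two of three classes with HbA1c above 7% and one class with normal values. This is a drafting gap that screeners at one site would be expected to fill from the labels and the Exclusion 2 definition. No bias, loss of precision or change of conclusion has been shown, and the number of subjects affected is unknown. The judgement rests on two assumptions: that screeners sort subjects by the named categories, and that the report describes the fasting glucose, HbA1c and OGTT values of those enrolled. It takes no position on which glycaemic limit is clinically right. No change to the plan is called for.

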## **Study protocol**

### *Screening*

[figure not shown]
Subjects will undergo evaluation at the Clinical Center for eligibility. This will include measurement of height, weight, waist circumference, blood pressure, and a detailed history and physical examination. Subjects will be screened for depression using the PHQ-9 questionnaire. If a subject is found to have severe depression or suicidal ideation, they will be seen by a psychiatrist at NIH on an emergent basis and further management will be guided by their recommendations. An electrocardiogram will be obtained to identify any subjects with QTc interval prolongation. Screening laboratory tests will include a serum pregnancy test for females, fasting plasma glucose, HgbA1c, OGTT (2 hour, after 75 g dextrose), comprehensive metabolic panel, CBC with differential, coagulation profile, midnight salivary cortisol, TSH, Free T4, FSH and LH levels. HIV 1&2 antibody and hepatitis C antibody levels will also be checked if on history taking the subject is found to have risk factors for HIV or Hepatitis C. A transvaginal ultrasound will be obtained to evaluate endometrial thickness in postmenopausal women (defined as amenorrhea for  $\geq 12$  months and an FSH level in the postmenopausal range) as well as those in the perimenopausal phase (amenorrhea for  $\geq 6$  months and FSH level in the postmenopausal range). An MRI Pelvis will be performed only if the transvaginal ultrasound is unable to provide an accurate measurement of the endometrial stripe. Subjects in whom a definite assessment of endometrial thickness cannot be obtained with either ultrasound or MRI (as may be the case in patients with multiple fibroids) will be followed closely for any signs of abnormal vaginal bleeding and will undergo a repeat transvaginal ultrasound upon completion of the study.

### *Study for eligible subjects*

This crossover study has two treatment arms (placebo or Mifepristone 50 mg tablets every six hours) with each subject serving as her own control. After eligibility is confirmed, subjects will undergo baseline testing and will be randomized to one of the treatment arms. Testing will be performed before and at the end of seven days of treatment with the study agent. Study drug will be continued until completion of post-drug testing. Thus, subjects will take the study drug for a total of nine days during each treatment arm. There will be a washout period of at least six and no more than eight weeks after which subjects will be randomized to the other arm of the study with an identical testing schedule. Subjects will record any symptoms or adverse events on a calendar

throughout the study. Women will be asked to keep a record of any abnormal menstrual bleeding. Subjects will be asked not to start on any new diet or exercise regimen during the study and maintain a stable weight for at least 2 weeks prior to study entry.

**Figure 1: Study Design overview**

*Procedures during each treatment*

Subjects will be admitted to the 5SWN metabolic unit or 5NW in the Clinical Center on a Sunday for testing the following day. To accommodate menstrual cycle timing, and for subjects for whom weekend testing is preferable, admission may occur on Friday or Saturday; additionally the Day 2 and 3 testing may be swapped if needed to accommodate nursing scheduling. To reduce potential variability associated with estrogen in premenopausal women, testing will be performed in the early follicular phase (days 1-7 of menstrual cycle). In case of perimenopausal women with irregular menstrual cycles, an attempt will be made to begin testing in the early follicular phase with the rest of the testing performed at pre-determined study intervals. Height, weight, and waist, hip and neck circumference (mean of three measurements) will be measured. Waist circumference will be measured at the intersection of midaxillary line with the uppermost lateral border of the right iliac crest at the end of a normal expiration (36). The hip circumference will be measured in a horizontal plane at the level of the maximal circumference of hips and buttocks. Neck circumference will be measured at mid-neck height between the mid-cervical spine and mid anterior neck to within 1 mm (37). Weight will be measured at the same time of the day on the same scale. All measurements will be taken after an overnight fast with the subject standing upright, both arms hanging loosely by the side of body, and eyes directed straight ahead. Subjects will be maintained on an isocaloric regular diet during the inpatient part of the study. Those subjects who are on metformin at the time of study entry will be maintained on the same dose of metformin throughout the study.

Day 1 (Monday)

- Fasting blood pressure will be measured consecutively three times five minutes apart. Blood pressure will be measured in a standardized manner in the morning using equipment that meets certification criteria. Measurements will begin after at least 5 minutes of rest in a supine position. Subjects will be asked to refrain from smoking or ingesting caffeine during the 30 minutes preceding the blood pressure measurement. Blood pressure will be measured in the same arm on

each occasion using an appropriate cuff size with the bladder in the cuff encircling at least 80 percent of the arm for accurate measurement.

- Morning fasting baseline laboratory measurements: serum levels of lipids (total cholesterol, HDL and low density lipoprotein (LDL) cholesterol, triglycerides, VLDL), glucose, total and free testosterone, androstenedione, DHEAS, comprehensive metabolic panel, ACTH and cortisol.
- ACTH and cortisol levels will be measured hourly for 24 hours from 0900h to 0900h the next day; urine will be obtained during this time for measurement of 5 alpha and beta-reduced cortisol metabolites, cortisol, cortisone and their tetra-hydro metabolites in collaboration with Dr. [name].
- Glucose levels will be measured before and two hours after breakfast, lunch, and dinner.

#### Day 2 (Tuesday):

Subjects will undergo an insulin-modified frequently sampled intravenous glucose tolerance test (FSIVGTT) when the urine collection is finished. Two indwelling intravenous catheters will be placed – one for sampling and other for infusing glucose and insulin. A bolus of 50% dextrose (0.3 gm/kg) will be administered over ~ 1 minute. Blood samples will be obtained for measurement of glucose, insulin, and free fatty acids (FFA) at -10, -1, 0, 1, 2, 3, 4, 5, 6, 7, 8, 10, 12, 14, 16, and 19 minutes. At 20 minutes, an insulin bolus (0.03 units/kg) will be administered and samples for insulin, glucose, and FFA will be collected at 22, 23, 24, 25, 27, 30, 40, 50, 60, 70, 80, 90, 100, 120, 150, and 180 minute time points. The data will be analyzed by Bergman method to calculate the insulin sensitivity index (Si) (38 - 39). Subjects will be allowed to go on pass if they can return by 8 AM.

A fasting lipid panel will also be obtained along with baseline labs.

#### Day 3 (Wednesday):

A 75 gram 3 hour OGTT with measurement of insulin, c-peptide and glucose levels at -5, 0, +30, +60, +90 +120, +150 and +180 min will be performed on day 3 before and after the study drug.

Serial blood draws for Day 1 (serial ACTH/cortisol measurements) and Day 3 (OGTT) will be obtained within 5 minutes of the appointed time. After the conclusion of Day 1 through Day 3 testing, subjects will be sent on pass with the study drug with instructions to begin at 6 PM, and to continue at 6-hour intervals.

#### Day 4 – 9:

Study participants will take the study drug as instructed for seven days and will return on day 10 of the study, bringing the remaining study medication with them. Study drug will be continued until all study procedures are complete on day 12 (study drug given for a total of 9 days).

Day 9 (Tuesday): Subjects will be readmitted to 5SWN or 5NW

#### Day 10 – 12 (Wednesday-Friday):

After an overnight fast, all study procedures indicated for day 1 -3 will be repeated on day 10 - 12. Blood (5 ml) will be obtained on day 10 for measurement of post-treatment mifepristone level and to hold for other potential measurements related to cortisol metabolism. Subjects will continue on the study drug until the completion of all study procedures on day 12.

Day 19 and 33 (Friday): Safety monitoring

After discontinuation of study drug, subjects will return approximately one week (Day 19) and then 3 weeks (Day 33) after the last day of study drug intake for measurement of blood chemistries and CBC. The research team will make every effort to ensure that these safety follow-up visits are within 2 days of day 19 and day 33. However, for subject convenience, we will allow for the follow-up visits to be within 5 days of the expected date of follow-up (day 19 ± 5 days and day 33 ± 5 days). In these cases, a member of the study team will contact the study subject on the expected date of follow-up to ensure that the subject is doing well. If any potential treatment-related abnormalities/adverse events are noted at the safety visits, subjects will receive appropriate treatment for these abnormalities and will be followed closely as clinically indicated until the abnormalities/adverse events have fully resolved.

Second study treatment visit: These study procedures will be repeated with each study drug after a wash-out period of 6-8 weeks.

For subject convenience, we will allow for the pre-study drug testing (Days 1 through 3) in each treatment arm to be done on days other than as specified above as long as it is done no more than 10 days prior to study drug initiation.

Table 1: Schema for first admission testing. The second admission will be identical.

Sunday	Monday	Tuesday	Wednesday	Thursday	Friday	Saturday
Admit to 5SWN or 5NW	DAY 1 Fasting labs 24 hr urine  0900 Serial 24 h ACTH/Cortisol  Pre & post prandial glucose levels	DAY 2 0900 Complete serial ACTH/Cortisol  0930 Fasting lipids FSIVGTT  Can go out on pass	DAY 3 0800 3 hr OGTT  1800 START MIFEPRISTONE OR PLACEBO	DAY 4 On pass	DAY 5 On pass	DAY 6 On pass
DAY 7 On pass	DAY 8 On pass	DAY 9 Return from pass to 5SWN	DAY 10 Fasting labs 24 hr urine  0900 Serial 24h ACTH/Cortisol  Pre & post prandial	DAY 11 0900 Complete serial ACTH/Cortisol  0930 Fasting lipids FSIVGTT	Day 12 3h OGTT STOP MIFEPRISTONE OR PLACEBO  Discharge	

			glucose levels			
					DAY 19 and 33 Follow-up	

Measurement of 11BHSD activity

Subjects will also undergo measurement of 11BHSD activity at least after one and no more than two months after the last day of study drug intake in the second treatment arm. This will be performed using 20% 9,11,12,12-[H]4-cortisol and 80% hydrocortisone, as reported by Andrew et al (kindly provided by [name]) (40). At time zero (~0830 h), a primed intravenous infusion of cortisol (20% 9,11,12,12-[H]4-cortisol and cortisol) is given (3.6 mg priming bolus, then continuous 1.74 mg/h infusion) for three hours and 20 minutes. Blood is obtained at times -5, 0, 60, 120, 180, 185, 190, 195 and 200 minutes. This test will only be performed once during the study. This part of the study is currently on clinical hold.

